## 5.6 Follow-up for dose-limiting toxicities

Patients whose treatment is interrupted or permanently discontinued due to an adverse event or clinically significant laboratory value, must be followed as outlined in Table 10, at least once a week for 4 weeks, and subsequently at 4-week intervals, until resolution or stabilization of the event, whichever comes first. If a patient requires a dose delay of > 14 days from the intended day of the next scheduled dose, then the patient should be discontinued from the treatment but will only come off study if dead or due to refusal to continue on the study. All patients must be followed for adverse events and serious adverse events for 28 days following the last dose of BKM120.

**Table 10: Follow-up for dose-limiting toxicities**

TOXICITY	FOLLOW-UP EVALUATION
Hematology	If $\geq$ CTCAE grade 3 neutropenia or $\geq$ CTCAE grade 3 thrombocytopenia have been demonstrated, these parameters must be repeated at least twice a week until resolution to $\leq$ CTCAE grade 1 neutropenia or $\leq$ CTCAE grade 1 thrombocytopenia to allow for initiation of re-treatment, and then at least weekly until either resolution or until stabilization.
Renal	If serum creatinine $\geq 2 \times$ ULN has been demonstrated, this parameter must be repeated at least twice a week until resolution to $\leq$ CTCAE grade 1 to allow for initiation of re-treatment, and then at least weekly until either resolution or until stabilization. If [+3] proteinuria, hematuria $\geq$ CTCAE grade 2 or serum creatinine $\geq 2.0 \times$ ULN has been demonstrated, a 24-hour urine collection for total protein and total creatinine must be repeated at least weekly until either resolution to baseline value or until stabilization. Whenever a measured CrCl is obtained, a serum creatinine should be obtained within $\leq 72$ hours of the urine collection.
Hepatic	If total bilirubin $\geq 2 \times$ ULN or $\geq$ CTCAE grade 3 AST/ALT has been demonstrated, these parameters must be repeated at least twice a week until resolution to $\leq$ CTCAE grade 1 (or $\leq$ grade 2 for AST or ALT, if liver metastasis are present) to allow for initiation of re-treatment, and then at least weekly until either resolution or until stabilization. Patients with total bilirubin $>$ ULN (any duration) should have fractionation of bilirubin into total/direct or indirect/direct components and any additional work-up as clinically indicated by these results. Follow-up of hyperbilirubinemia should proceed as per the guidelines above, irrespective of the results of fractionation.
Metabolic/Laboratory	If amylase and/or lipase $\geq$ CTCAE grade 3 ( $> 2 \times$ ULN) has been demonstrated, these parameters must be assessed once at 2 to 4 days and once again at 7 days ( $\pm 1$ day) and be repeated twice a week until resolution to $\leq$ CTCAE grade 2 to allow for initiation of re-treatment, and then at least weekly until either resolution to $\leq$ CTCAE grade 1 or until stabilization. A CT scan or other imaging study to assess the pancreas, liver, and gallbladder must be performed within 1 week of the first occurrence of any $\geq$ CTCAE grade 3 of amylase or lipase. In patients with serum triglycerides $\geq 500$ mg/dL, urine amylase needs to be tested in addition.
Endocrine (no CTCAE grading; refer to Table 15 for definition of grades)	For details of the follow-up and treatment of $\geq$ grade 2 hyperglycemia refer to Table 15.

TOXICITY	FOLLOW-UP EVALUATION
Cardiac	
Patient who experience QTc prolongation should be followed as per Table 11.
 
In addition, patients who experience ECG abnormalities indicative of an ischemic cardiac event, ECGs should be repeated at least twice a week until normalization or stabilization of ECG findings.
 
If troponin <math>\geq</math> CTCAE grade 3 has been demonstrated, this parameter must be repeated twice a week until resolution to <math>\leq</math> CTCAE grade 1 to allow for initiation of re-treatment, and then at least weekly until either resolution or until stabilization.

Neurotoxicity	
Patients who experience neurotoxicity should be followed as per Table 11.

Mood alteration
 
<math>\geq</math> grade 2
 
Note: For grade 2 Anxiety only, if worsened from baseline
	
For patient who experience <math>\geq</math> grade 2 mood alteration a psychiatrist must be consulted for diagnosis and determination of most appropriate medical treatment. Patients must be followed twice weekly by patient self-rating mood scale and be seen weekly by the psychiatrist until resolved <math>\leq</math> grade 1 or baseline (for anxiety).
 
Continue to test weekly by mood scale until resolution to baseline or stabilization
 
Refer to Table 12 for more details.


Non-Laboratory
 
Rash
	
Patients who experience non-laboratory DLTs must be evaluated at least once a week following demonstration of the toxicity until resolution of the toxicity to allow for re-treatment, stabilization of the toxicity, or study treatment completion
 
Whenever a rash is diagnosed, the following should be obtained:
 
 
• A paired skin biopsy from both an affected and an unaffected skin area for local histopathology assessment
 
• A plasma sample to assess the concentration of BKM120
 
 
For the follow up of skin rash, refer to Table 6

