
a ≥ CTCAE grade 3 anemia will not be considered DLT unless judged to be a hemolytic process secondary to study drug. ≥ CTCAE grade 3 lymphopenia will not be considered DLT unless clinically significant.
 
b For any grade 3 or 4 hepatic toxicity that does not resolve within 7 days to ≤ grade 1 (or ≤ grade 2 if liver infiltration with tumor present), an abdominal CT scan has to be performed to assess if it is related to disease progression.
 
A single patient is assumed not to tolerate the dose if he/she experiences at least one DLT. If a lower grade AE leads to a dose interruption of more than 7 doses of BKM120, this AE will be considered as DLT.
 
If the 2nd occurrence of an initially non-dose limiting toxicity (e.g., grade 3 AST that resolved to ≤ grade 1 within 7 days at 1st occurrence) leads to a dose reduction ( Section 6) within 28 days of the first dose of BKM120, this will be considered a DLT.
	

The investigator must notify the sponsor immediately of any unexpected ≥ CTCAE grade 3 adverse events or laboratory abnormalities. Prior to enrolling patients into a higher dose level, ≥ CTCAE grade 2 adverse events will be reviewed for all patients at the current dose level.

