## 6. DOSING DELAYS/DOSE MODIFICATIONS

**Table 11: BKM120 dose level modification guidelines: Criteria for interruption and re-initiation of BKM120 treatment**

Recommended Dose Modifications for BKM120	
Worst toxicity (CTCAE Grade)**	Recommended Dose Modifications
No toxicity	Maintain dose level
HEMATOLOGICAL	
Neutropenia (ANC)	
Grade 1 (ANC < LLN – 1.5 x 10  /L) Grade 2 (ANC < 1.5 – 1.0 x 10  /L)	Maintain dose level
Grade 3 (ANC < 1.0 – 0.5 x 10  /L) Grade 4 (ANC < 0.5 x 10  /L)	Omit dose until resolved to ≤ Grade 1, then: 
 
• If resolved in ≤ 7 days, then maintain dose level
 
• If resolved in > 7 days, then ↓ 1 dose level
 

Febrile neutropenia (ANC < 1.0 x 10  /L, fever ≥ 38.5°C)	Omit dose until resolved, then ↓ 1 dose level
Thrombocytopenia	
Grade 1 (PLT < LLN – 75 x 10  /L) Grade 2 (PLT < 75 – 50 x 10  /L)	Maintain dose level
Grade 3 (PLT < 50-25 x 10  /L)	Omit dose until resolved to ≤ Grade 1, then: 
 
• If resolved in ≤ 7 days, then maintain dose level
 
• If resolved in > 7 days, then ↓ 1 dose level
 

Grade 4 (PLT < 25 x 10  /L)	Omit dose until resolved to ≤ Grade 1, then ↓ 1 dose level

Recommended Dose Modifications for BKM120	
Worst toxicity (CTCAE Grade)**	Recommended Dose Modifications
HEPATIC	
Bilirubin (*for patients with Gilbert Syndrome these dose modifications apply to changes in direct bilirubin only)	Will be fractionated if elevated
Grade 1 (> ULN – 1.5 x ULN)	Maintain dose level with LFTs* monitored as per protocol
Grade 2 (> 1.5 – 3.0 x ULN) with ALT or AST ≤ 3.0 x ULN	Omit dose until resolved to ≤ Grade 1, then: 
 
• If resolved in ≤ 7 days, then maintain dose level
 
• If resolved in > 7 days, then ↓ 1 dose level
 

Grade 3 (> 3.0 – 10.0 x ULN) with ALT or AST ≤ 3.0 x ULN	Omit dose until resolved to ≤ Grade 1, then: 
 
• If resolved in ≤ 7 days, ↓ 1 dose level
 
• If resolved in > 7 days discontinue patient from study treatment
 

Grade 4 (> 10.0 x ULN)	Omit dose and discontinue patient from study treatment
AST or ALT	
Grade 1 (> ULN – 3.0 x ULN)	Maintain dose level with LFTs* monitored as per protocol

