Grade 3	
Omit dose until resolved to <math>\leq</math> Grade 1, then <math>\downarrow</math> 1 dose level (co-medicate)
 
Note: If question 9 on the PHQ-9 has a positive response, or worsens in severity, the patient should be referred for psychiatric consult regardless of the total questionnaire score

Grade 4	
Omit dose and discontinue patient from study
 
Note: If question 9 on the PHQ-9 has a positive response, or worsens in severity, the patient should be referred for psychiatric consult regardless of the total questionnaire score

Rash	
Grade 1	Maintain dose level. Consider to initiate appropriate skin toxicity therapy (such as antihistamines, topical corticosteroids)
Grade 2	Maintain dose level. Initiate/intensify appropriate skin toxicity therapy (such as antihistamines, topical corticosteroids)
Grade 3	
Omit dose until resolved to CTCAE Grade <math>\leq</math> 1, then:
 
 
If resolved in <math>\leq</math> 7 days, <math>\downarrow</math> 1 dose level
 
If resolved in <math>></math> 7 days (despite appropriate skin toxicity therapy), discontinue patient from BKM120
 

Grade 4	Omit dose and discontinue patient from BKM120
Fatigue (asthenia)	
Grade 1 or 2	Maintain dose level
Grade 3	
Omit dose until resolved to <math>\leq</math> Grade 1, then:
 
 
If resolved in <math>\leq</math> 7 days, maintain dose level
 
If resolved in <math>></math> 7 days, <math>\downarrow</math> 1 dose level
 

Grade 4	Omit dose and discontinue patient from BKM120
Other non-hematological adverse events	
Grade 1 or 2	Maintain dose level
Grade 3	Omit dose until resolved to $\leq$ Grade 1, then $\downarrow$ 1 dose level
Grade 4	
Omit dose and discontinue patient from study
 
Note: Omit dose for <math>\geq</math> Grade 3 vomiting or Grade 3 nausea only if the vomiting or nausea cannot be controlled with optimal antiemetic

Pneumonitis	See Table 15
** Common Terminology Criteria for Adverse Events (CTCAE) version 4.0.	

Fasting Plasma Glucose (FPG)	

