## Management of Liver Toxicities

**Monitoring: every week** (if visit schedule allows a more frequent monitoring this should be considered) or more frequently if clinically indicated especially for patients with borderline acceptable AST/ ALT/ bilirubin\* values.

In case of any occurrence of ALT/ AST/ bilirubin\* increase  $\geq$  **grade 3** the liver function tests must be monitored **weekly** or more frequently if clinically indicated **until resolved to  $\leq$  grade 1**; hereafter the monitoring should be continued **every other week** or more frequently if clinically indicated **until the end of treatment with study medication**.

Patients who discontinued study treatment should be monitored weekly, including LFTs\* or more frequently if clinically indicated **until resolved to  $\leq$  grade 1 or stabilization** (no CTCAE grade change over 4 weeks).

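### Tables 10 and 11 give different BKM120 hold and restart rules for creatinine and amylase/lipase, so one laboratory course can count as a DLT under one table and not the other

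*Combined protocol and SAP*

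**What the plan says.** Table 11 (Section 6) is described as giving "Criteria for interruption and re-initiation of BKM120 treatment". It has rows for neutropenia, thrombocytopenia, bilirubin, AST/ALT, fasting glucose, cardiac events, mood, rash, fatigue and pneumonitis. Creatinine and amylase/lipase have none. The only row that can take them is "Other non-hematological adverse events": dose kept at grade 1 or 2; at grade 3 held until grade 1 or lower, then cut by one level; at grade 4 stopped.

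Table 10 (Section 5.6) covers both. Creatinine of at least 2 x ULN is repeated until it is no higher than "CTCAE grade 1 to allow for initiation of re-treatment, and then at least weekly until either resolution or until stabilization". Grade 3 amylase or lipase is followed until it is no higher than "CTCAE grade 2 to allow for initiation of re-treatment, and then at least weekly".

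Section 5.5 interrupts BKM120 for a toxicity that is a DLT or a potential DLT, unless specified otherwise. Its named exceptions are grade 2 hyperglycemia and grade 2 mood alteration. Section 5.4 sends interruption and modification of dosing to Table 9; Section 5.14 repeats the sentence but names Table 11.

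The notes to Table 9 add: "If a lower grade AE leads to a dose interruption of more than 7 doses of BKM120, this AE will be considered as DLT".

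**The concern.** A site that sees a creatinine or lipase rise finds two rules for the same event and no statement of which prevails. Normally that would be a dosing ambiguity only. Here the number of missed doses is itself a DLT criterion, so the ambiguity reaches the primary endpoint. The MTD is set by counts in cohorts of three to six, where a single DLT changes the decision in Table 7. The renal case is foreseeable: Section 5.8.2 lists creatinine elevation as a cisplatin effect, and dose levels 1 to 3 in Table 8 raise cisplatin alone.

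**Working it through.** **1. The rules side by side**

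| Event | Section 5.5 and Table 10 | Table 11, other non-hematological row |
|---|---|---|
| Creatinine at least 2 x ULN, grade 2 | Held if a potential DLT; restart at grade 1 or lower | Dose maintained |
| Amylase/lipase grade 3 | Restart at grade 2 or lower | Held to grade 1 or lower, then one level down |

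For creatinine the conflict is over whether to hold. For amylase/lipase it is over when to restart, and whether to reduce.

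**2. Renal course.** Creatinine is 2.2 x ULN on day 0 and 1.8 x ULN on days 4 to 12.
- Table 9 needs 2.0 to 3.0 x ULN for more than 7 consecutive days. If 2.2 persists until the day 4 result, the value is in range on days 0 to 3, which is 4 days. 4 is not above 7, so this criterion is not met.
- Section 6.1 places values above grade 1 at 1.5 x ULN or more, so 1.8 x ULN is not yet grade 1.
- Section 5.5 with Table 10: held from the day after the day 0 result, days 1 to 12, one dose a day = 12 missed doses. 12 > 7, so a DLT.
- Table 11: grade 2, dose maintained = 0 missed doses. No DLT.

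**3. Lipase course.** Grade 3 for 5 days, grade 2 for 6 days, then grade 1, with one dose missed per day held.
- Table 9 needs grade 3 not back to grade 2 or lower for more than 7 days. 5 is not above 7, so this criterion is not met.
- Table 10: 5 missed doses, not above 7. No DLT.
- Table 11: 5 + 6 = 11 missed doses, above 7. A DLT if the seven-dose rule covers this event.
- In general the two readings differ when grade 3 days are 7 or fewer and grade 3 plus grade 2 days exceed 7.

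The two examples go in opposite directions: Table 10 gives the extra DLT for creatinine, Table 11 for lipase.

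**4. Effect on escalation.** Section 13's table follows from Table 7: P(escalate) = (1-p)^3 + 3p(1-p)^2 x (1-p)^3. At p = 0.20 this is 0.512 + 0.384 x 0.512 = 0.709, against the stated .71. At 30, 40, 50 and 60% it gives .494, .309, .172 and .082, against .49, .31, .17 and .08. All are reproduced.

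One reclassified patient turns 0/3 (escalate) into 1/3 (add three patients), or 1/6 (escalate) into 2/6 (stop; previous level is the MTD).

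The share of patients with such a course is not given. As an assumed range, if the reading added 2, 5, 10 or 15 percentage points to a 20% DLT rate, P(escalate) would fall from .71 to .67, .60, .49 or .40.

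**The case against.** The best defence is that there is a governing table. Section 5.14 and the title of Table 11 assign interruption and restart to it. Table 10 is a follow-up table for patients already interrupted, and Section 5.5 yields where something else is specified, so Table 11's instruction to maintain could be that specification. This is a fair reading, but not a settled one: Section 5.4 uses the same sentence and points to Table 9, and Section 5.5 names its exceptions without mentioning creatinine. Nor do Section 6.1's cisplatin adjustments and Section 5.1's rule that BKM120 continues when cisplatin is held say what happens to BKM120 for the creatinine value itself.

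A second defence is that both courses are constructed to miss a Table 9 duration criterion, and that events of grade 2 or higher are reviewed before escalation. This stands as a limit on size. The review does not, however, say which holds count.

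A third is that Section 5.12.11 treats a laboratory value as an adverse event only if it causes symptoms, is clinically significant or needs therapy, whereas the Table 11 row and the seven-dose rule both speak of adverse events. This also stands, as a condition on the DLT result. The conflict in dosing instructions remains, because Section 5.5 expressly covers abnormal laboratory values.

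A reader might infer two stronger points that the documents do not support:
- **Pancreatitis also flips.** It does not. Table 10 has no pancreatitis row, and Table 9 makes grade 2 or higher a DLT outright. What remains is that Section 5.5 interrupts for it while the Table 11 row maintains the dose at grade 2; the DLT count is unaffected.
- **Liver monitoring is contradictory.** Table 10 asks for tests at least twice a week; the liver section in 7.1 asks for weekly tests or more often if clinically indicated. Testing twice a week satisfies both.

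**Conclusion.** Wrong as written, moderate severity. The hold rule for creatinine of at least 2 x ULN and the restart rule for grade 3 amylase/lipase each appear in two incompatible forms, and the governing table is unclear. Through the seven-dose rule, a course that misses Table 9's own duration criterion can be a DLT under one table and not under the other: 12 against 0 missed doses in the renal example, 5 against 11 in the lipase example.

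The renal result assumes that 2.2 x ULN is grade 2 (the upper limit of grade 2 is not printed; if it lay below 2.2, Table 11 would not maintain the dose). It also assumes that the value is a potential DLT, a term the protocol does not define, and that it counts as an adverse event under Section 5.12.11. The lipase DLT result needs that last condition too. In addition, the lower grade wording must cover a grade 3 event that fell short of its own criterion, and Table 9's general row for grade 3 or higher events must not already capture it. The conflict over restart needs none of these DLT-counting assumptions.

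It would be wrong to infer that Section 13's escalation probabilities are in error. They are correct for a given DLT rate; what is not fixed is which events count toward that rate.

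**What to change.** The sponsor should reconcile Sections 5.4, 5.5 and 5.14 and Tables 9, 10 and 11 for creatinine and amylase/lipase, so that each has one hold rule and one restart rule wherever it appears. The protocol should state which table governs BKM120 holds and restarts, so that the seven-dose count rests on one consistent set of rules. It should also say what a potential DLT is, and whether the seven-dose rule reaches a grade 3 laboratory event that did not meet its own duration criterion. Section 5.5 and the Table 11 row should be aligned for grade 2 pancreatitis, for consistency only.

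Which thresholds to adopt is for the sponsor; no view is taken here. The seven-dose rule should not be narrowed to particular toxicities as part of this, since that would be a new clinical rule. The cost is protocol wording, with no added patients or procedures.

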## **5.7 Monitoring of BKM120 suspected toxicities**

Patients whose treatment is interrupted or permanently discontinued due to an adverse event or clinically significant laboratory value, must be followed as outlined in Table 10, at least once a week for 4 weeks, and subsequently at 4-week intervals, until resolution or stabilization of the event, whichever comes first. If a patient requires a dose delay of > 14 days from the intended day of the next scheduled dose, then the patient should be discontinued from study treatment. If the patient requires more than 2 dose reductions, the patient should be discontinued from study treatment. All patients must be followed for adverse events and serious adverse events for 28 days following the last dose of BKM120. All SAEs must be reported to Novartis as detailed in section 5.12.11 and 5.12.12.

## **5.8 Agent Administration**

### **5.8.1 BKM120 Administration**

The study drug BKM120 will be self-administered (by the patients themselves). The investigator will instruct the patient to take the study drug exactly as specified in the protocol. BKM120 will be administered on a continuous once daily dosing schedule. Patients should be instructed to take the dose of BKM120 daily in the morning, one hour after a light breakfast (morning meal) at approximately the same time each day. BKM120 should be taken with a glass of water and consumed over as short a time as possible. Patients should swallow the capsules as a whole and not chew them. Do not crush capsule. Patients should continue to fast for 2 hours after the administration of each BKM120 dose.

If vomiting occurs during the course of treatment, no re-dosing of the patient is allowed before the next scheduled dose. The occurrence and frequency of any vomiting during a treatment must be noted as an adverse event. In addition, on the days of full pharmacokinetic sampling, the exact time of any episodes of vomiting within the first 4 hours post-dosing on that day and within the first 4 hours following the previous day's dosing must be noted whenever possible.

If the patient forgets to take her/his dose AFTER 6:00 PM, then the dose should be withheld that day and BKM120 should be restarted the following day.

Patients must avoid consumption of St. John's Wort, Seville oranges, grapefruit or grapefruit juice, grapefruit hybrids, pummelos and exotic citrus fruits from 7 days prior to the first dose of study medication and during the entire study treatment period due to potential CYP3A4 interaction with the study medication. Patients must avoid concomitant intake of strong and moderate CYP3A4/5 inhibitors and inducers. Orange juice is allowed.

All dosages prescribed and dispensed to the patient and all dose changes during the study must be recorded. If a patient requires a BKM120 dose delay of >14days from the previous dose, the patient must be discontinued from treatment but will only come off study if dead or due to refusal to continue on the study. Patients will only require a 28 day follow up visit after the last dose of BKM120.

Medication labels will comply with US legal requirements and be printed in English. They will supply no information about the patient. The storage conditions for study drug will be described on the medication label.

### **5.8.2 Cisplatin Treatment**

Commercially available supplies of cisplatin will be used for this study. Preparation instructions can be found in the FDA approved package insert. Cisplatin will be administered per institutional guidelines.

Cisplatin injection is a sterile, aqueous solution, available in 50ml, 100ml, and 200ml, multiple dose vials, each ml containing 1mg of Cisplatin and 9mg sodium chloride in water for injection. HCl and/or sodium hydroxide added to adjust pH to 3.5 to 4.5. It will be given intra-venously (IV) on days: (1, 8, 15, 22, 29, 36 and 43).

If radiation is held, BKM120 and cisplatin will be held as well. Additional weekly chemotherapy treatments may be added to the treatment course if chemo/XRT was held during the course of treatment. Cisplatin should be given only if at least 3 more days of radiotherapy treatment remain. Days of chemotherapy may be changed (+/-) 2 days if unforeseen circumstances require the timing of treatment. Treatment doses are based on body surface area (BSA). The actual body weight will be used for dose calculations as long as the BSA is below 2. For a BSA above 2, the BSA will be capped at 2.

Cisplatin is nephrotoxic and the patients will receive pre-and post treatment hydration according to institutional standards.

Institutional guidelines for highly emetogenic regimens will be followed. Patients will receive a 5HT antagonist for primary prevention of nausea and vomiting and will also receive 8 mg of dexamethasone IV according to institutional standards. The patients may receive a 5HT antagonist and decadron per IV on day 2 and 3 after chemotherapy for delayed nausea at the discretion of the investigator. The concomitant use of aprepitant and BKM120 is not allowed.

- Possible side effects of cisplatin are
  - Hematologic: Neutropenia, anemia, thrombocytopenia
  - Gastrointestinal: Nausea, vomiting
  - Dermatologic: Alopecia
  - Renal: Elevation of blood urea nitrogen (BUN) and Creatinine, hypomagnesemia, hypokalemia, hypocalcemia
  - Neurologic: Peripheral neuropathy, restlessness
  - Allergic reactions
  - Ototoxicity

Cisplatin is a commercially available product that is provided as part of standard of care.

